Pilot study of Powered Exoskeleton Use for Gait Rehabilitation in Individuals with Multiple Sclerosis

PI: [name]
Co-investigators: [name]
[name]
[name]

Date: April 17, 2019

Version: 1.0

Background

Powered exoskeletons are approved by the FDA to assist in the rehabilitation of persons with spinal cord injury and post-stroke hemiplegia, but not multiple sclerosis (MS). We are aware of only one pilot study of a powered exoskeleton (ReWalk®) in MS. Thirteen persons with MS and EDSS 5.5 to 7.0 were enrolled, and 5 were able to tolerate the device. Skin issues were the most frequent adverse event. Qualitative improvement of sitting, standing, and walking posture was noted in those who used the device consistently. We are not aware of any study of the EksoBionics GT exoskeleton in MS.

Device

The EksoGT is a powered motorized orthosis intended to enable individuals who are experiencing muscular or neurological conditions affecting their lower extremities to perform ambulatory functions such as gait training. (See Figures 1 and 2.) It consists of a fitted metal brace that supports the legs, feet, and torso. It is adjustable to accommodate different length segments and different hip widths. Typically, a physical therapist straps the patient's feet, legs, and torso into the device. Soft goods (pads, spacers, straps, and supports) are available for bracing and adapting to various body types. The straps and soft goods are specifically designed to prevent pressure points or other skin issues. There is also a link (Don-Doff Link) just below each hip joint, which permits abducting the legs while seated to facilitate donning and doffing the device.

Figure 1: The EksoGT in use during gait training of an SCI patient.

[figure not shown]

Figure 2: The EksoGT structure and general dimensions.

The EksoGT manipulates the patient's legs and waist to stand up, walk over level ground, and then to sit down. Battery powered motors drive knee and hip joints. The batteries are designed to last for

approximately three hours of normal use. The patient is required to assist with balance and body positioning using a cane, crutches, or walker, which are provided with the device. The physical therapist operates the device and monitors the patient to ensure balance is maintained. The device is operated in various modes. In some modes, steps are triggered with the attached user interface. In other modes, steps are triggered when the machine is in certain target postures. In other modes, the therapist may adjust the level of assistance provided so that, if the patient has some residual strength, the patient performs some of the walking motion with their own muscles.

The EksoGT has a number of features to ensure patient safety. It is equipped with mechanical hard stops at the limits of healthy Participant ranges of motion to prevent powering the joint of the user to a position that the joint cannot reach. The actuated range of motion at the hip is -20° to 135° and the actuated range for the knee is 0° to 120°. Not all of this range of motion is needed in normal walking; however the ranges of these joints were selected to provide for other necessary functions such as standing and sitting. At the ankle the device is passive, with springs to resist sagittal plane motion, and locked in the other degrees of freedom. The range of motion provided at the ankle is from -10° to 20° dorsiflexion with hard stops at the limits of this range to protect the user and a setting to specify the neutral angle.

Redundant position sensing on all of the actuated joints ensures that the motors are always controlled using reliable sensor information. In addition, the device has numerous sensor, motor, and software monitoring systems. If any abnormality is detected (i.e. excess joint speed or force, or if redundant sensors do not agree) the device enters a safe mode, which prevents continued walking and enables the physical therapist to safely remove the patient. The device is also equipped with fail-safe brakes on the actuated knee joints, such that if the device loses power or is shut down for any reason the knees will continue to support the patient. Finally, an emergency disable button is available to instantly shut down the device for any reason. This is implemented via hardware, so it is effective even during a software malfunction.

All study physical therapists will be trained to using the study device by the manufacturer. The training will be conducted at our facility.

Aims

1. To assess the feasibility and safety of using the EksoBionics GT exoskeleton for gait training in patients with relapsing or progressive MS and severe mobility limitations (EDSS 5.5 – 7.5).
2. To collect preliminary efficacy outcomes on gait and walking for the purpose of designing a larger clinical trial of the EksoBionics GT exoskeleton for gait training in patients with MS.

Methods

Design: uncontrolled pre-post intervention study

Participants:

Sample size: up to 15 participants will be enrolled, with the goal of 5 participants completing the study period.

Inclusion/exclusion criteria

Inclusion criteria	Exclusion criteria

 Diagnosis of MS per 2017 revised McDonald criteria EDSS score 5.5-7.5 (moderate to severe walking disability) Cleared for gait training with the study device by the study treating physician 
Device-Specific Criteria
 
 Involved in a standing program or must be able to tolerate at least 15 min upright without signs or symptoms of orthostatic hypotension Weigh 220 pounds (100kg) or less Be able to fit into the Ekso device: Between approximately 5'0" and 6'4" tall (really depends on leg measurements) Sufficient diaphragmatic strength such that respiration is not compromised with exercise 
Assessed by physical therapy:
 
 Standing hip width of approximately 18" or less Have near normal range of motion in hips, knees and ankles Sufficient upper extremity strength to use a front wheeled walker by manual muscle testing (minimum triceps strength bilaterally of 3/5, shoulder abduction and flexion/extension of 4/5 OR as discussed during demo, 2 normally functioning limbs such as in hemiplegia) 	
 MS exacerbation, severe acute comorbidity or surgery less than 90 days prior to enrollment Diagnosed with osteoporosis or history of long bone fractures since diagnosis Safety concern due to neurologic impairments (e.g. upper extremity weakness, visual loss) or comorbidities (e.g. cardiac, respiratory) Other neurologic or non-neurologic condition interfering with walking < 1 month since previous intensive gait training regimen or initiation of treatment that can affect walking (e.g. medication for spasticity) Planned change in medications that may affect walking during the study period Uncontrolled or severe orthostatic hypotension that limits standing tolerance Active heterotrophic ossification (HO), hip dysplasia, or uncontrolled hip/knee axis abnormalities Score <22 on the Mini-Mental State Examination or deemed to have cognitive impairment precluding safe training with the device during the screening and training process Colostomy Pregnancy Unresolved deep vein thrombosis Uncontrolled autonomic dysreflexia Currently involved in another rehabilitation study 
Assessed by physical therapy:
 
 Severe spasticity that prevents joint motion (severe stiffness or rigidity) in proximal lower extremity muscles, including hip adductors and knee flexors/extensors. Hip flexion contracture greater than ~17° Knee flexion contracture greater than 12°

	
 • Unable to achieve neutral ankle dorsiflexion with passive stretch (achieve neutral with up to 12° knee flexion) • Leg length discrepancy greater than 0.5" for upper leg, greater than 0.75" for lower leg • Spinal instability (TLSO may be worn in device with physician clearance) • Severe muscular or skeletal pain • Open skin ulcerations on buttocks or other body surfaces in contact with exoskeleton or harness • Shoulder extension ROM < 50° excludes using crutches during sit to stand or vice versa. (Walking with crutches permitted, sit <> stand would be done with walker.)
--	---

Data collected

Demographic and clinical data: age, sex, duration of MS symptoms in years, MS course (relapsing or progressive), use of assistive device to walk indoors / outdoors (none, unilateral, bilateral), Body Mass Index, concomitant medications

Screening	Expanded Disability Status Scale Mini-Mental State Examination
Safety	Adverse events during or between rehabilitation sessions (particularly falls and musculoskeletal pain) Pain severity on Numeric Pain Rating Scale and pain location
Feasibility	Percentage of patients who complete at least 75% of the training sessions. Percentage of patients who drop out of the study
Acceptability	assistive device subscale of the Quebec User Evaluation of Satisfaction with Assistive Technology questionnaire v.2 (https://www.sralab.org/rehabilitation-measures/quebec-user-evaluation-satisfaction-assistive-technology)
Efficacy (tested without device)	Spasticity (Modified Ashworth Scale) Hip flexor strength (handheld dynamometer) Gait parameters : - GAITRite system (overground gait mat): velocity, cadence, step length, step width, double support time (averaged between left and right when appropriate) - CAREN system (treadmill with harness): gait kinematics

	Timed 25 Foot Walk 2-minute Walk Test MS Walking Scale-12
--	---

The **Expanded Disability Status Scale (EDSS)** is a comprehensive, quantitative neurological examination, and is the most widely used measure of MS-related disability for clinical and research purposes. The order of the exam may vary slightly among providers, but generally the patient undergoes a complete neurologic examination, then completes up to a 500 meter walk (with or without an assistive device) which involves walking the length of our 50 meter clinic hallway 10 times. The examiner notes the distance the patient is able to walk, along with the presence of an assistive device, if applicable.

The **Mini Mental State Examination (MMSE)** is an 11-question measure that tests five areas of cognitive function: orientation, registration, attention and calculation, recall, and language. Widely used in clinical practice, the MMSE will be administered in this study to screen for severe cognitive impairment that precludes safe participation.

The **Numeric Pain Rating Scale** evaluates pain by asking the patient to situate the severity of pain experienced on a 0-10 level scale (from no pain to maximal pain). In addition, the patient will be asked to report the location of the pain. A publication from a cross-sectional study using the NRS on 236 MS patients with pain proposed the following cutoff scores: 0-2 : mild, 3-5 : moderate, 6-10 : severe.1 Pain will be assessed as a safety measure.

The **Quebec User Evaluation of Satisfaction with Assistive Technology (QUEST) questionnaire v.2** is a new outcome measurement instrument designed to evaluate a person's satisfaction with his or her assistive technology device. It can be used with adolescents, adults and elderly persons who as a result of a physical or sensory impairment have acquired an assistive technology device. The QUEST 2.0 was created for assistive technology practitioners and researchers. As a clinical tool, the QUEST 2.0 provides practitioners with a means of collecting satisfaction data that can be used to document the real-life benefits of assistive technology and to justify the need for these devices. As a research tool, it can be used to compare satisfaction data with other outcome measures such as clinical results, quality of life, functional status, cost factors and comfort

The **Modified Ashworth Scale (MAS)**: the Ashworth scale, first published in 1964, grades resistance to passive mobilization on a 5-level ordinal scale. The psychometric properties of the Ashworth scale are well documented, and even though this tool has been criticized for its lack of inter-rater reliability, it is still the most widely used measure of spasticity in clinical trials. The modified version of the Ashworth scale, which allows one intermediate grade, will be used for this study. We will evaluate the following muscle groups: hip adductors, knee flexors, and knee extensors. The MAS scores for all muscle groups in both legs will be averaged.

Hip Flexor Strength will be measured bilaterally with a hand-held dynamometer (the Lafayette Manual Muscle Testing System, Lafayette IN). This device provides a digital display of the force generated by active muscle contraction. Two measurements of peak strength will be taken on each side, and the average of the measurements will be calculated. Hand-held dynamometry was found more reproducible and sensitive to change than the manual muscle test grading system.

The **GAITRite electronic walkway** is a computerized gait analysis system consisting of a 30-foot mat with embedded sensors and a data acquisition and processing software. The GAITRite has been used to analyze gait patterns in various neurologic populations, including MS. The spatiotemporal gait parameters analyzed include stride length, double support time, base of support (step width), and the functional ambulation profile (FAP) score.

[figure not shown]
The **Computer Assisted Rehabilitation ENvironment (CAREN)** system is installed in the Mellen Center building and routinely used for patient care and clinical research. The hardware includes: a 6 degrees of freedom motion base on which sits a 3-meter diameter platform with a dual belt instrumented treadmill; a 10-camera real-time motion capture system; a 120-degree cylindrical screen projection system with surround sound; wireless EMG and 3 high-speed cameras. The CAREN system creates an immersive virtual environment with real-time feedback loop, causing the system to respond to subject motion. The software allows to define inputs, perturbations and sensory disturbances, for research and training purposes. Gait data is continuously recorded and analyzed offline using the Gait Off-Line Analysis Tool. The CAREN system is staffed with two trained operators, who are also developers for the system.

The **Timed 25 Foot Walk (T25FW)** is part of the Multiple Sclerosis Functional Composite (MSFC), an outcome measure for MS therapeutic trials. This test has been widely used to measure walking speed in MS. The patient is instructed to walk 25 feet as quickly as possible, but safely. Two trials are conducted, and the average time is calculated.

The **2-Minute Walk (2MW)** has been validated in cardiovascular and respiratory disease, in lower limb amputation, and has been used in neurorehabilitation trials in stroke and multiple sclerosis. The subject is asked to walk as far as possible and as fast as possible (but safely) for 2 minutes in a 50-meter hallway. The timer will not be stopped if the patient takes brief rest periods during the walk. If the test is discontinued before 2 minutes, either by patient request or evaluator decision, the time and reason for stopping will be noted.

The **MS Walking Scale-12** (MSWS-12) is a disease-specific instrument gathering subject-reported information about the impact of MS on their walking ability, designed for use in clinical practice and clinical research. The MSWS-12 contains 12 questions with a recall period of 2 weeks. The psychometric properties of the MSWS-12 have been extensively evaluated in diverse MS populations in both community and hospital settings, with demonstration of internal consistency, high reliability and validity, and good generalizability.

Evaluation schedule

All assessments will be performed at T1, T2, and T3. In addition, a phone visit will be conducted 4 +/- 1 weeks after treatment initiation to review adverse events, adherence to treatment sessions, and any comments / questions the participants may have.

All participants will be invited to participate in the T2 assessment visit, even if they have decided to terminate treatment for various reasons.

Treatment

The rehabilitation treatment will consist of 3 sessions per week for 8 weeks, for a total of 24 sessions. Missed sessions will be made up if possible. Each session will be scheduled for 60 minutes, and will consist of stretching, overground gait training, and gait training with the study device. Rest periods will be provided as necessary during the training visits.

Statistical analysis

Patient characteristics will be summarized using frequencies and percentages for categorical factors and means and standard deviations or medians and quartiles for continuous measures. The percentage of participants meeting established MDC or MCID for any of the outcome measures will also be calculated. Change over time in functional outcomes will be evaluated using linear mixed effect models. In these models, each functional measure will be the outcome and time point will be the predictor. Repeated measures within subject will be models assuming an autoregressive or spatial correlation structure. Estimated changes with 95% confidence intervals will be summarized for each measure. Outcomes measured bilaterally will be averaged for analysis primarily. Incidences and types of adverse events will be summarized overall and by time period. Adherence to training sessions will be summarized descriptively using means and standard deviation and the percentage of patients achieving minimum completion standards will also be described. Analysis will be performed using SAS software (version 9.4, Cary, NC).

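### Device satisfaction (QUEST) is scheduled before any device use and has no collection point when a participant stops early, so acceptability could come mainly from those who tolerated the exoskeleton

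*Combined protocol and SAP*

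**What the plan says.** - **Visit rule.** The Evaluation schedule states: "All assessments will be performed at T1, T2, and T3". There is no assessment-by-visit table, and T1, T2 and T3 are not defined.
- **Acceptability measure.** The Acceptability row of Data collected contains one item: "assistive device subscale of the Quebec User Evaluation of Satisfaction with Assistive Technology questionnaire v.2". It names neither a visit nor the device to be rated. The description of the questionnaire says that its respondents "have acquired an assistive technology device".
- **Design.** Methods describes an "uncontrolled pre-post intervention study".
- **Early stoppers.** The Evaluation schedule says: "All participants will be invited to participate in the T2 assessment visit, even if they have decided to terminate treatment". No such invitation is stated for T3. The phone contact about 4 weeks after treatment starts covers adverse events, adherence and comments, but not QUEST.
- **Expected completion.** Methods plans at most 15 enrolled and aims for 5 completers. Background cites a pilot of a different exoskeleton in which 5 of 13 tolerated the device.
- **Analysis.** Statistical analysis models change for functional outcomes only and names no QUEST analysis. It also plans to count participants who reach an MDC or MCID on any outcome measure.
- **Screening measures.** The Screening row of Data collected reads "Expanded Disability Status Scale Mini-Mental State Examination", which sits awkwardly with the all-visits rule.

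**The concern.** QUEST asks how satisfied a person is with a device they have used. A score taken before use is not a baseline for that construct. Because the rated device is not named, a participant with a cane or walker could reasonably answer about that aid.

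The larger problem lies at the other end. People who stop early probably include those who found the device least acceptable. They have no QUEST at the point of stopping. They get one at T2 only if they return, and they may then be recalling a few sessions from weeks before. Feasibility and safety are the first aim, and aim 2 looks ahead to a larger trial. A satisfaction score drawn mostly from people who tolerated the device would give that trial an optimistic picture.

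**Working it through.** The plan states no figure for QUEST, so there is nothing to reproduce. The check sets the text side by side and then illustrates the size.

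**1. Is T1 before device use?** The visits are undefined, so this is an inference. The design is pre-post, which requires a measurement before treatment. T2 is offered to people who have already ended treatment, so T2 falls during or after the course. That leaves T1 as the natural baseline. The all-visits rule then places QUEST at T1.

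**2. How long could recall be?** The course is 8 weeks (3 sessions a week, 24 in total). If T2 falls at the end of the course (assumed), someone who stops at the end of week 1 answers about 8 − 1 = 7 weeks later.

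**3. How far could the mean move?** Let p be the share who stop early, a the share of stoppers who complete QUEST at T2, and g the amount by which stoppers score lower. Assume that all who continue respond and that the stoppers who attend are typical of stoppers.

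- Mean over all users, relative to those who continue: −p·g
- Mean over respondents: −[p·a / (1 − p + p·a)]·g
- Upward bias: [p − p·a / (1 − p + p·a)]·g

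Inputs: p = 8/13 = 0.615, from the pilot in Background, treating non-tolerance as stopping early (assumed). g = 0.5 to 1.5 points (assumed; the documents give no QUEST distribution).

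| Stoppers completing QUEST at T2 | Multiplier of g | Bias, g = 0.5 | Bias, g = 1.5 |
|---|---|---|---|
| None | 8/13 = 0.615 | 0.31 | 0.92 |
| Half (4 of 8) | 8/13 − 4/9 = 0.171 | 0.09 | 0.26 |
| All | 0 | 0 | 0 |

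**4. Does it depend on the borrowed rate?** Using this plan's own target, 15 enrolled and 5 completing, p = 10/15 = 0.667. With no stopper attending, the bias is 0.33 to 1.00. With half attending, the multiplier is 10/15 − 5/10 = 0.167 and the bias is 0.08 to 0.25. The picture is the same. It assumes full enrolment and that every non-completer used the device at least once.

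**5. Could a T1 score enter the analysis?** The mixed models are for functional outcomes, so QUEST change is not modelled. The MDC/MCID sentence covers any outcome measure, so a T1-based QUEST change is not ruled out.

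**The case against.** The best defence is that a T1 QUEST does little harm. No QUEST change model is planned, and an uninformative T1 score does not damage T2 or T3 scores. It matters only if T1 scores are pooled, or used for change under the MDC/MCID sentence, and the plan specifies neither. This stands, and it is why the point rests mainly on early stoppers.

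On early stoppers, the plan does invite everyone to T2, so the case in which none attend is a worst case. The score gap is assumed, and the 5 of 13 rate belongs to another device. The plan also reports the dropout percentage under Feasibility, so readers will see how many stopped. All of this is fair, and it is why the size is given as a range running down to zero. It does not supply what is missing: the stoppers' own rating, taken near the time of use. Full attendance at T2 would remove the selection but not the delay.

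A reader might also infer that the all-visits rule distorts walking change, because the EDSS includes a walk of up to 500 m that could tire participants before the timed walks. The documents do not support that. They do not say that the EDSS walk is on the same day as the timed walks, comes before them, or lacks rest between tests. If it is repeated at every visit, as the rule says, an equal burden largely cancels in within-person change. A spurious gain would need the EDSS walk before the timed walks at T1 only, which contradicts the rule. No bias figure is claimed here.

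**Conclusion.** The concern holds for QUEST. Followed literally, the schedule collects device satisfaction when it most plausibly cannot be rated, and has no collection point when a participant stops early. Acceptability *could* therefore come mainly from those who tolerated the device. The documents do not show that it *will*, because that depends on who accepts the T2 invitation.

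The illustrative overstatement is 0.3 to 0.9 points if no stopper attends T2 and about 0.1 to 0.3 if half attend. It rests on an assumed gap of 0.5 to 1.5 points, on 8 of 13 stopping, and on T1 being before device use. It would be too strong to say that the T2 and T3 scores are invalid.

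The mismatch between the Screening label for EDSS and MMSE and the all-visits rule, and the absence of a test order, are secondary schedule clarifications.

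**What to change.** **Main change**
- Define T1, T2 and T3, and replace the blanket sentence with an assessment-by-visit table.
- Do not give QUEST at T1.
- Name the EksoGT on the form as the device to be rated.
- Give QUEST at T2 and T3. For anyone who stops early, also give it at the last device session, or as soon as possible after stopping.
- Summarise QUEST over everyone who used the device at least once, and report how many responded among those who continued and those who stopped.
- State that no T1-based QUEST change will be computed under the MDC/MCID sentence.

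**Secondary clarification**
- Say whether EDSS and MMSE are for screening only or are repeated.
- Complete eligibility screening before the T1 tests, preferably on an earlier day.
- Use the same test order and rest between tests at every visit.

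**Cost.** Schedule wording, plus one short questionnaire for each participant who stops early. Dropping QUEST at T1 saves one questionnaire per participant. An earlier screening day could add a visit for some, which is why it is a preference only.

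### Does the unstated random part, correlation structure and degrees-of-freedom method of the mixed model make the T3 interval wrong enough to change the plan?

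*Combined protocol and SAP*

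**What the plan says.** The Statistical analysis section is the whole analysis plan. On functional outcomes it states: "Change over time in functional outcomes will be evaluated using linear mixed effect models". Visit is the only covariate named, and the dependence within a participant is described thus: "Repeated measures within subject will be models assuming an autoregressive or spatial correlation structure". The output is given as "Estimated changes with 95% confidence intervals will be summarized for each measure". SAS 9.4 is named, but no procedure or option.

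The section names no random effect, no rule for choosing between the two structures, no spatial function and no degrees-of-freedom method. No other section supplies them. The Evaluation schedule says "All assessments will be performed at T1, T2, and T3", and the text available gives no calendar times for these visits.

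Under Participants, the size is "up to 15 participants will be enrolled, with the goal of 5 participants completing the study period". The second aim is "To collect preliminary efficacy outcomes on gait and walking for the purpose of designing a larger clinical trial".

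**The concern.** With so few participants, the covariance model and the degrees of freedom largely set the width of each interval. Two analysts could both follow the section faithfully and report different precision from the same data.

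One reading is also misspecified in a plausible case. Fitted as a residual structure with no random intercept, AR(1) forces the T1-T3 correlation to be the square of the adjacent one. Stable differences between participants keep that correlation higher, so the model overstates the uncertainty of T3-T1. The intervals are the only inferential output defined for functional change, and the outcomes are meant to inform a larger trial. An interval that is too wide for no good reason could therefore matter.

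**Working it through.** The documents state no correlation, interval width or precision target, so there is no figure of the plan's own to reproduce. Size (5 to 15), three time points and the 95% level come from the documents. Correlations, visit times, equal variances and dropout patterns are assumptions.

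**1. Large-sample algebra, equal spacing.** With total variance s² and adjacent correlation ρ, AR(1) alone gives Var(T3-T1) = 2s²(1-ρ²)/n. If the true correlation is r at every lag, the true variance is 2s²(1-r)/n, and the fitted ρ tends to r. The ratio of standard errors is √[(1-r²)/(1-r)] = √(1+r). For T2-T1 it is √[(1-r)/(1-r)] = 1, so that interval is unaffected.

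**2. Five participants, complete data.** These are REML simulations with constant true correlation and 2(n-1) = 8 degrees of freedom for AR(1) and compound symmetry (CS), 4 for paired t. T3-T1 half-widths are in baseline SD units.

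| r | √(1+r) | AR(1) | CS | Paired t | AR/CS | AR/paired | AR(1) coverage |
|---|---|---|---|---|---|---|---|
| 0.7 | 1.30 | 0.96 | 0.78 | 0.91 | 1.23 | 1.05 | 98.0% |
| 0.8 | 1.34 | 0.82 | 0.64 | 0.74 | 1.28 | 1.11 | 98.4% |
| 0.9 | 1.38 | 0.60 | 0.45 | 0.52 | 1.33 | 1.15 | 98.6% |

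The excess is about 24% to 33% over CS and 6% to 15% over paired t; one-point differences from the table are rounding. At r = 0.5, AR(1) is no wider than paired t (ratio 0.99). T2 coverage is 94% to 95%.

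**3. With a random intercept.** Under constant correlation, CS (equivalent to a random intercept) covers 93.8% to 95.8% for n from 5 to 15. With a random intercept plus AR(1) residuals at n = 5 and r = 0.9, the half-width is 0.47 if the autocorrelation is held non-negative, with coverage of 95% to 96%. The excess of AR(1) alone is then 0.60/0.47 = 1.28. Allowing negative autocorrelation gives 0.42, but coverage falls to 91% to 93%, so that is not a fair yardstick.

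**4. If the correlation decays.** Under a true AR(1), the AR(1) interval covers 93.8% to 96.2% and CS only 89.7% to 92.2%. Under a random intercept plus AR(1) errors, AR(1) alone covers 96.0% to 98.2%.

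**5. Degrees of freedom.** At n = 5 the multiplier is 2.306 with 8 degrees of freedom and 1.960 with a normal reference, a ratio of 2.306/1.960 = 1.18. With the normal multiplier, AR(1) alone under constant correlation 0.5 to 0.9 covers 95.6% to 97.5% at T3.

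**6. What a replacement would do.** Dropout is taken as unrelated to outcome.

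- With 15/10/5 or 15/15/5 participants at T1/T2/T3, AR(1) alone has a T3 standard error 8% to 17% too large and covers 97% to 98%.
- Unstructured covariance with Kenward-Roger covers 87% to 90% at T3 in those patterns, and 90% to 93% with 10/8/5.
- Paired t covers 94% to 96%. With 15 falling to 5, its T3 interval is about 5% to 19% wider than AR(1) under constant correlation, and about 44% to 56% wider under true AR(1) decay.
- With five complete participants, unstructured equals paired t and widens the T2 interval by about 17%, although AR(1) was already calibrated there under constant correlation.

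**The case for a change.** The strongest argument for acting is that naming the random part, one structure and the degrees of freedom takes two sentences and stops the choice being made after the results are seen. It is also true that the error is not always conservative:

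- If participants differ in response (assumed variance 0.2), AR(1) covers 91% to 93% at T2.
- Under a spatial power structure with T2 at week 8 and T3 at an assumed week 12, 20 or 32, T2 coverage is 97% to 98%, 93%, and 89% to 91%.
- With more complete participants the excess over paired t grows, to 17% to 26% at n = 8.

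The omissions are real and these figures stand. They do not show a wrong interval, because each needs an assumption the documents neither make nor exclude: no random intercept, a given correlation pattern, a given visit spacing or a given spread of response. A mixed-effects model ordinarily carries a participant random effect, and with one the T3 excess largely goes.

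Nor do they point to one better analysis. CS under-covers if the correlation decays. Unstructured covariance under-covers with the attrition that the enrolment target allows for. Paired t discards participants without T3, whom the mixed model keeps. The Evaluation schedule tries to limit such loss at T2 ("All participants will be invited to participate in the T2 assessment visit, even if they have decided to terminate treatment for various reasons") but makes no such statement for T3. A rule that switches to paired t when many lack T3 would need a threshold and would itself be a data-dependent choice.

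**Conclusion.** No change to the plan follows. The section leaves out detail that an analyst would settle sensibly when programming, and the available alternatives trade one error for another.

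The worst case at T3 in the equal-spacing, five-completer setting is coverage of 98% to 99% in place of 95%, with an interval 6% to 15% wider than paired t or 24% to 33% wider than CS. That rests on AR(1) without a random intercept, constant correlation of 0.7 to 0.9, complete data and 8 degrees of freedom. T2 under-coverage arises only under the further assumptions listed above.

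The consequence is small. This is a single-arm pilot whose first aim is feasibility and safety. No hypothesis test, precision target or decision rule depends on the T3 width, and with complete data the estimated changes are the same under every structure considered. The reported results need only name the covariance model and degrees of freedom used, and give the number measured at each visit, for a reader planning the larger trial to judge the intervals.
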